9.4.1.4 Urinalysis

Test items: Specific gravity, pH, and qualitative measurements (glucose, protein, urobilinogen, and occult blood)

Visit: [Evaluation period] Weeks 0, 2, 4, 6, 8, 10, 12, 14, 16, 18, 20, 22, and 24, and at the time of discontinuation

[Extended administration period] Weeks 8, 12, 16, 20, 24, 28, 32, 36, 40, 44, 48, and 52, at the first visit following dose increase or resumption after interruption, and at the time of discontinuation

9.4.2 Vital Signs and Other Tests

The following tests will be performed, and the date of measurement and test results will be entered into the eCRF. The tests in Week 0 will be performed before the first administration of the study drug. The

allowable window for the timing of measurement of test items will be within 4 days before and after the scheduled visit dates during the period from Week 2 to Week 24, and within 7 days before and after the scheduled visit dates thereafter.

9.4.2.1 Height

Test item: Height

Visit [allowable window]: At the time of screening [from the time of obtaining consent until before the start of study drug administration (Week 0)]

9.4.2.2 Weight

Test item: Weight

Visit: Weeks 0, 24, and 52, and at the time of discontinuation

9.4.2.3 Vital Signs

Test items: Blood pressure, pulse rate, and body temperature (axillary)

Visit: [Evaluation period] Weeks 0, 2, 4, 6, 8, 10, 12, 14, 16, 18, 20, 22, and 24, and at the time of discontinuation

[Extended administration period] Weeks 8, 12, 16, 20, 24, 28, 32, 36, 40, 44, 48, and 52, at the first visit following dose increase or resumption after interruption, and at the time of discontinuation

9.4.3 Standard 12-Lead Electrocardiogram (ECG)

A standard 12-lead ECG will be performed and the following items will be entered into the eCRF.

- Date of ECG
- Result or finding of ECG

If there are any findings, it will be determined whether or not the findings are clinically problematic (interpretation: normal or abnormal, not clinically significant/abnormal, clinically significant), and will be entered into the eCRF.

Test items: Basic waveform, QT interval, and QTc

However, if the above items are not measurable due to atrial fibrillation or the like, such a measurement failure will not be handled as a deviation.

Visit: [Evaluation period] Weeks 0*, 2, 4, 6, 8, 10, 12, 14, 16, 18, 20, 22, and 24, and at the time of discontinuation

[Extended administration period] Weeks 8, 12, 16, 20, 24, 28, 32, 36, 40, 44, 48, and 52, at the first visit following dose increase or resumption after interruption, and at the time of discontinuation

*: Performed before the first administration of the study drug.

Allowable window: Within 4 days before and after the scheduled visit dates during the period from Week 2 to Week 24, and within 7 days before and after the scheduled visit dates thereafter

9.4.4 Pregnancy Test

Test item: Pregnancy status*

Visit: At the time of screening, Week 52, and at the time of discontinuation

*: Female subjects only. However, no pregnancy test is required if at least 12 months have passed since the last menstrual period without any other medical reason.

9.4.5 Drug Concentration Measurement

9.4.5.1 Plasma KHK7580 Concentrations

Plasma KHK7580 concentrations will be measured. Residual samples after measurement of plasma drug concentrations may be used for the analysis of KHK7580 metabolites that is not planned in this study. Drug concentration data from this study may also be combined with data from other studies for population pharmacokinetic analysis.

9.4.5.2 Blood Collection Method and Sample Processing Method

Venous blood (2 mL) will be collected in a vacuum blood collection tube containing EDTA-2K, and mixed promptly by inverting the tube. The plasma obtained by centrifugation will be divided into two equal portions and dispensed into two sample tubes. The plasma samples will be frozen immediately after dispensing, and cryopreserved at -20°C or below until the start of measurement.

The date and time of blood collection (date/time of specimen collection) and the date and time when the study drug was taken (see Section 9.3.1) will be entered into the eCRF.

9.4.5.3 Blood Collection Time Points

Visit of blood collection [allowable window]:

Weeks 0 (before the first administration of the study drug, and 0.5 hours [\pm 10 minutes], 1 hour [\pm 10 minutes], 2 hours [\pm 15 minutes], and 3 hours [\pm 15 minutes] after the first administration of the study drug), 2, 4, 8, 12, 16, 20, and 24, after the end of the evaluation period* (0.5 hours [\pm 10 minutes], 1 hour [\pm 10 minutes], 2 hours [\pm 15 minutes], and 3 hours [\pm 15 minutes] after administration of the study drug)

*: If a subject transitions to the extended administration period before Week 24, blood collection will be performed in any one of Week 4, 8, 12, 16, 20, or 24. Subjects should come to the hospital without taking the study drug on the day when plasma drug concentration measurement after the end of the evaluation period is performed.

Blood collection may be omitted if a subject was not taking the study drug as of the day before the day of blood collection. It is also permissible not to perform post-dose blood collection in a subject for whom a decision to interrupt study drug administration has been made on the day of blood collection.

9.4.5.4 Measurement Method and Test Plan

Plasma drug concentration measurement will be performed at the Technical Solution Headquarters, using its own established LC/MS/MS method. Prior to the measurement, the study director at the company's headquarters will prepare a test plan for concentration measurement.

9.4.5.5 Method for Transportation of Plasma Samples

will take charge of collecting samples taken at study sites for drug concentration measurement. The company will forward frozen samples to

Study sites, , and will store records of sample transfer and related information.

9.4.5.6 Reporting of Measurement Results

The final report on measured plasma drug concentrations will be prepared by and submitted to the sponsor.

9.5 Adverse Events

9.5.1 Definition of Adverse Events

An adverse event is defined as any undesirable medical incident that occurs in a subject receiving the study drug. This refers to any unwanted or unintended signs (including abnormal changes in clinical laboratory values), symptoms, or diseases that occur when the study drug is administered, whether or not they are causally related to the study drug. Adverse drug reactions are defined as adverse events that are judged to be either “related” or “possibly related” in terms of their causal relationship to the study drug. In patients with parathyroid carcinoma, exacerbation of the primary disease and accessory symptoms are not considered adverse events.

For laboratory test items (hematology and blood biochemistry), the presence or absence of deviation (abnormal value) will be checked based on the reference values at each study site; if an abnormal value is observed, it will be judged whether the change is clinically problematic (abnormal change) as compared with the value before the start of study drug administration. However, changes in intact PTH levels, Ca levels, and corrected serum Ca levels will be handled as abnormal changes if such changes cannot be explained from the pharmacological perspective as judged by the investigator or subinvestigator in view of the pharmacological action of KHK7580.

For signs, symptoms, and abnormal changes in clinical laboratory values associated with a specific disease (diagnostic name), the diagnostic name will be adopted as the adverse event term. However, in cases where signs or symptoms that are atypical for a specific disease, or extremely severe signs and symptoms develop, each of these signs and symptoms, as well as the diagnostic name, will be handled as adverse events.

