6.2 Inclusion Criteria

Subjects enrolled in this study should satisfy all of the following criteria.

- 1) Personally submitted written voluntary informed consent to participate in the study
- 2) Aged \geq 20 years at the time of consent
- 3) A diagnosis of parathyroid carcinoma or PHPT who are unable to undergo PTx or relapse after PTx
- 4) Corrected serum Ca level > 11.3 mg/dL at screening

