9.5.2 Definition of Serious Adverse Events

“Serious adverse event” refers to an adverse event that falls under any of the following conditions.

However, hospitalization for examination and hospitalization planned in advance are exceptions.

- 1) Results in death
- 2) Is life-threatening
- 3) Requires inpatient hospitalization or causes prolongation of existing hospitalization
- 4) Results in persistent or significant disability/incapacity (in the opinion of the reporter)
- 5) Is a congenital anomaly
- 6) Other medically significant conditions

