11.1.2.2 Reporting to the Parties Concerned

11.1.2.2.1 Reporting of Serious Adverse Events

- 1) If a serious adverse event occurs, the investigator or subinvestigator will immediately (within 24 hours of learning of the event’s occurrence) report the event to the Emergency Safety Information Reception Center or the sponsor, either orally, by telephone, email, or fax (using Attachment 4 “Serious Adverse Event Report (First Report)” of the protocol (supplementary volume) or in the form specified by the study site), regardless of whether the event is causally related to the administration of the study drug.
- 2) Afterwards, the investigator will also submit a Serious Adverse Event Report (Detailed Report) to the sponsor and the head of the study site within 7 days after he/she becomes aware the event’s occurrence. In doing so, the investigator will report to the head of the study site by identifying any serious unexpected adverse drug reaction.
- 3) The investigator will also provide additional information as requested by the sponsor, the head of the study site, and the IRB.
- 4) The head of the study site will consult the IRB as to whether the study may be continued at the study site.

Emergency contact

Emergency Safety Information Reception Center

Tel.: (pronounced as “*shikyu fukusayo*” in Japanese, meaning urgency and adverse drug reaction); fax:
Reception hours: 24 hours (seven days a week)

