13.1.2 Safety Evaluation

The incidence of each adverse event and adverse drug reaction that occurred or worsened after the start of study drug administration will be calculated. Calculation of the incidence of each adverse event and adverse drug reaction will be performed based on the MedDRA PT and SOC.

With regard to laboratory parameters and vital sign values, summary statistics will be calculated for each evaluation time point.

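### In parathyroid carcinoma subjects, events attributed to the disease fall outside the adverse-event definition, so even a death or unplanned admission gets no seriousness or causality assessment, triggers no serious-event report and is absent from the event tables

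*Combined protocol and SAP*

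**What the plan says.** The study enrols two diagnoses under one criterion (section 6.2): "A diagnosis of parathyroid carcinoma or PHPT who are unable to undergo PTx or relapse after PTx". Section 9.5.1 first defines an adverse event broadly, without regard to cause. It then says that in patients with parathyroid carcinoma "exacerbation of the primary disease and accessory symptoms are not considered adverse events". No similar sentence exists for PHPT.

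Three definitions or rules build on that one:

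- Section 9.5.1: "Adverse drug reactions are defined as adverse events that are judged to be either" related or possibly related to the study drug.
- Section 9.5.2: a serious adverse event "refers to an adverse event that falls under any of the following conditions", the first of which is death. Admissions for tests and admissions already scheduled are exempt.
- Section 11.1.2.2.1: "If a serious adverse event occurs, the investigator or subinvestigator will immediately (within 24 hours" of learning of it) report it. A detailed report within 7 days and IRB consultation follow.

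The planned event analysis in section 13.1.2 is: "The incidence of each adverse event and adverse drug reaction that occurred or worsened after the start of study drug administration will be calculated", by MedDRA preferred term and system organ class.

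Section 9.5.1 has two further clauses that bear on the exclusion. Changes in intact PTH, Ca and corrected Ca "will be handled as abnormal changes if such changes cannot be explained from the pharmacological perspective". And where the presentation is unusual for the diagnosis, "or extremely severe signs and symptoms develop, each of these signs and symptoms, as well as the diagnostic name, will be handled as adverse events". Neither clause mentions the carcinoma exclusion.

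**The concern.** Keeping disease progression out of the adverse-event tables can be defended when progression is captured elsewhere as an outcome. Here it is not. The endpoints in section 3.2 are calcium, PTH, adverse events, laboratory values, vital signs, pharmacokinetics and EQ-5D-5L; none is progression or survival. Yet long-term safety over 52 weeks is a stated objective (sections 3.1.2 and 7.1.2).

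The design has no comparator (section 4), so no control rate can separate disease from drug. What counts as an event in a carcinoma subject depends on the attribution made by an investigator who also sets the dose. Because the attribution is made before the event reaches the adverse-event form, a drug contribution to the worsening would not be assessed on that form either. The exclusion also applies to one diagnosis only, so the same symptom may count in a PHPT subject and not in a carcinoma subject.

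**Working it through.** The plan gives no figure on this point, so the check is mainly a reading of the definitions in sequence. Take a carcinoma subject who dies, is admitted unexpectedly or develops a symptom, and whose investigator attributes this to the carcinoma.

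1. **Adverse event?** No, by the carcinoma sentence in 9.5.1. No limit by severity or outcome is stated.
2. **Serious adverse event?** No. Under 9.5.2 it must first be an adverse event.
3. **Adverse drug reaction?** No. Under 9.5.1 it must first be an adverse event.
4. **Seriousness, fatal outcome and causality recorded?** Not on the adverse-event form. Section 9.5.4 lists these as adverse-event items.
5. **Expedited report?** No. Section 11.1.2.2.1 is triggered by a serious adverse event, and 11.1.2.2.2 covers only other adverse events.
6. **In the event tables?** No. Section 13.1.2 counts adverse events and adverse drug reactions.

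**What remains on record**

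- Corrected Ca, intact PTH and whole PTH by time point (13.1.1.2), and laboratory and vital-sign summaries (13.1.2).
- Date of and reason for withdrawal (12.1.2), with action taken and subsequent course (17.3).
- Reasons for dose reduction or interruption (9.3.1).
- Concomitant drugs with indication, and therapies for the underlying disease (7.2).

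None of these carries a seriousness or causality judgement or triggers a serious-event report. A non-fatal unplanned admission that does not lead to withdrawal is the least well covered.

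**The three rules in 9.5.1 side by side**

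| Situation in a carcinoma subject | Carcinoma exclusion | Other clause in 9.5.1 |
|---|---|---|
| Ca rise not explained by the drug's pharmacology | Not an adverse event, if judged exacerbation | Abnormal change |
| Atypical or extremely severe sign of the disease | Not an adverse event | Adverse event |
| Death or admission from ordinary progression | Not an adverse event | Not clearly covered |

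The text does not say which rule prevails in the first two rows.

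**Scale (illustration only)**

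The input is the target of at least 10 treated subjects (13.2). I assume exactly 10 and use exact (Clopper-Pearson) two-sided 95% intervals.

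- 0/10 shown: the upper limit is 1 − 0.025^(1/10) = 30.8%.
- 1/10 if one excluded event were counted: 10%. The lower limit is 1 − 0.975^(1/10) = 0.3% and the upper limit is 44.5%.
- 2/10 if two were counted: 20% (2.5% to 55.6%), against 0/10 shown.

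The chance of at least one such event among m carcinoma subjects with per-subject risk p is 1 − (1 − p)^m. The documents give neither m nor p, so both are assumptions:

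| p | m = 5 | m = 10 |
|---|---|---|
| 5% | 1 − 0.95^5 = 22.6% | 1 − 0.95^10 = 40.1% |
| 10% | 1 − 0.90^5 = 41.0% | 1 − 0.90^10 = 65.1% |
| 20% | 1 − 0.80^5 = 67.2% | 1 − 0.80^10 = 89.3% |

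The column m = 10 supposes that every subject has carcinoma and is the upper end for a study of 10.

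**The case against.** - **Some excluded events may come back in.** A rise in Ca on a Ca-lowering drug arguably meets the test of being unexplained by pharmacology, and a life-threatening presentation may count as extremely severe. This stands in part. A reader might infer that an admission for hypercalcaemia is definitely not an adverse event; the text leaves that open. But the clause on severe signs reads as a rule for choosing the event term, and it does not clearly reach a death or admission from ordinary progression.
- **Accessory symptoms can be read narrowly.** The phrase may mean worsening of existing disease symptoms, so that new symptoms are not excluded. The text allows both readings, which is a reason to define the term.
- **These events are recorded elsewhere.** A reader might infer that they appear in no planned output and are lost for good. The documents do not support that: calcium and PTH summaries, withdrawal reasons and drug records leave traces, and a disease death or a withdrawal for progression can be found. What is missing is assessment, serious-event reporting and a place in the event tables.
- **The detailed analysis plan may add a deaths listing or a split by diagnosis.** Section 13.1 gives only the main analyses, and section 13.6 defers details to a plan finalised by database lock. So pooling of the diagnoses is not shown to be final; section 13.1.2 simply specifies no split. A later plan could not by itself supply seriousness and causality judgements that were never made.
- **The 10% versus 0% contrast follows from n = 10.** This is correct. It would hold for any single missed event and is no evidence that one is likely.
- **Separating progression from adverse events is a deliberate choice.** That is so, and the main table can stay as planned. The choice does not require that fatal or serious events go unassessed.

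**Conclusion.** The concern holds within stated limits. It affects only carcinoma subjects, and only events that the investigator attributes to the disease. For those events, 9.5.1, 9.5.2, 9.5.4, 11.1.2.2.1 and 13.1.2 together remove seriousness and causality assessment, serious-event reporting and tabulation, with no exception for death or unplanned admission. Following the rule as written can only lower the tabulated event incidence, in a small study without a comparator that has a long-term safety objective.

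The size cannot be derived from the documents, because neither the number of carcinoma subjects nor their risk of such events is given. Each subject whose only event of a kind is excluded lowers that incidence by 10 percentage points if 10 are treated. Calcium, PTH, laboratory and vital-sign summaries and the primary efficacy analysis do not depend on the adverse-event definition.

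A reader might go further and infer that drug-related deaths are being hidden. The text does not support that: the exclusion concerns disease worsening, and the point is that a possible drug contribution to it goes unassessed. This should be corrected, but it does not invalidate the study.

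**What to change.** 1. In 9.5.1, define accessory symptoms and state how the carcinoma exclusion, the Ca/PTH clause and the clause on atypical or extremely severe signs fit together.
2. Record the excluded events on the adverse-event form, including seriousness and causality, with a flag for events judged to be primary disease.
3. Tabulate incidence with and without flagged events, and by diagnosis (carcinoma, PHPT). The sponsor's main table can remain the one without them.
4. List all deaths and unplanned hospitalisations in every subject whatever the attribution, keeping the 9.5.2 exemptions for admissions for tests and those scheduled beforehand.
5. State how flagged fatal or serious events are to be reported.

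The cost is one eCRF flag, some more event entries, one extra table and one listing. If flagged serious events enter the expedited flow, there is added work for the 24-hour and 7-day reports and for IRB consultation. The recording step has to be in place while data are collected, because traces elsewhere in the eCRF cannot fully replace assessments that were never made.

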9.5.2 Definition of Serious Adverse Events

“Serious adverse event” refers to an adverse event that falls under any of the following conditions.

However, hospitalization for examination and hospitalization planned in advance are exceptions.

- 1) Results in death
- 2) Is life-threatening
- 3) Requires inpatient hospitalization or causes prolongation of existing hospitalization
- 4) Results in persistent or significant disability/incapacity (in the opinion of the reporter)
- 5) Is a congenital anomaly
- 6) Other medically significant conditions

9.5.3 Definition of Other Significant Adverse Events

“Other significant adverse events” are defined as all events, except serious adverse events, that result in discontinuation or interruption of study drug administration or in dose reduction.

9.5.4 Items to Be Investigated

Information from the start of study drug administration to Week 52 (or at the time of discontinuation) will be entered into the eCRF for the following items.

Adverse events will be followed until they have been reversed to their state before study drug administration, or until the investigator or subinvestigator determines that follow-up is no longer necessary based on the subject's condition, including symptoms, findings, and laboratory values.

- 1) Reported term for the adverse event
- 2) Start date of adverse event
- 3) Severity/intensity
 - Mild: Signs or symptoms are present but do not interfere with daily activities.
 - Moderate: Discomfort interferes with daily activities or there is an impact on the clinical condition
 - Severe: Daily activities are impossible or there is a significant impact on the clinical condition
- 4) Seriousness (serious event)
 - Serious (Yes): Events that correspond to the definition in Section 9.5.2
 - Non-serious (No): Events that do not correspond to the definition in Section 9.5.2
- 5) Action taken with study treatment
 - Dose not changed
 - Dose reduced
 - Drug interrupted
 - Drug withdrawn
 - Not applicable
- 6) Other actions: Action other than that taken with study treatment (other action taken)
 - None
 - Other drugs
 - Other
- 7) Outcome of adverse event
 - Recovered/resolved
 - Recovering/resolving
 - Not recovered/not resolved
 - Recovered/resolved with sequelae
 - Fatal
 - Unknown
- 8) End date of adverse event
- 9) Causal relationship with the study drug (causality)

The causal relationship with the study drug will be classified into the following three categories.

For "not related," the reason for the judgment will be entered into the eCRF.

- Not related
- Possibly related
- Related

9.6 Number of Blood Collections and the Volume of Blood Collected

Total number of blood collections: 29 times

Total volume of blood collected: 234 mL

As a guide, the prespecified number of blood collections and the volume of blood collected during the study participation period are shown in Table 9.6-1 and Table 9.6-2. The total number of blood collections and the total volume of blood collected have been calculated on the assumption that subjects will complete the evaluation period in Week 24 and go through the extended administration period until Week 52. However, the total number of blood collections and the total volume of blood collected may increase in cases where screening is carried out more than once and where a post-dose-increase (or post-resumption) visit occurs during the extended administration period. The total number of blood collections and the total volume of blood collected may also increase if additional/follow-up examination is performed in consideration of the safety of a subject.

Table 9.6-1. Breakdown of the volume of blood collected (informed consent - evaluation period)

	Screening	Time after the start of administration (Weeks)														At the time of discontinuation	
		0				2	4	6	8	10	12	14	16	18	20	22	
Time after administration (h)	Before administration	0.5	1	2	3												
Hematology	-	2	-	-	-	2	2	2	2	2	2	2	2	2	2	2	2
Blood biochemistry 1	2	4	-	-	-	4	4	4	4	4	4	4	4	4	4	4	4
Blood biochemistry 2	-	4	-	-	-	4	4	4	4	4	4	4	4	4	4	4	4
Plasma drug concentration	-	2	2	2	2	2	2	2	-	2	-	2	-	2	-	2	-
Total volume of blood collected	2	12	2	2	2	12	12	10	12	10	12	10	12	10	12	10	10

Table 9.6-2. Breakdown of the volume of blood collected (extended administration period)

	Time after the start of administration (Weeks)														At the first visit following dose increase or resumption after interruption	At discontinuation		
	8	12	16	20	24	After the end of the evaluation period				28	32	36	40	44	48	52		
Time after administration (h)						0.5	1	2	3									
Hematology	2	2	2	2	2	-	-	-	-	2	2	2	2	2	2	2	2	2
Blood biochemistry 1	4	4	4	4	4	-	-	-	-	4	4	4	4	4	4	4	4	4
Blood biochemistry 2	4	4	4	4	4	-	-	-	-	4	4	4	4	4	4	4	4	4
Plasma drug concentration	2	2	2	2	2	2	2	2	2	-	-	-	-	-	-	-	-	-
Total volume of blood collected	12	12	12	12	12	2	2	2	2	10	10	10	10	10	10	10	10	10

